Aim 2.1. We will utilize the raw data collected during Phase II to develop regression models, under both ON and OFF medication states for all contact pairs. The top panel in Figure 2 presents the overview of Aim 2.1; the goal of this sub-Aim is to predict the gait parameters for patients on low frequency by using the gait sensor measurements obtained on high frequency. Additional independent variables/regressors include general patient/disease characteristics such as age, gender, and disease duration. We will also build models under both ON and OFF medications. To develop the regression models, we use non-linear regression analysis based on random forest (RF) classifier. RF is based on an ensemble of decision trees, referred to as a 'forest,' where predictions for any new observation are obtained from averaging the predictions of individual trees (56). Generally, RF models are not prone to overfitting and are robust against noisy or high-dimensional datasets (57). In addition, they are generally interpretable, allowing for further examination of results and easier subject subtyping with respect to symptomology. However, to assure that the RF based models are the best performing models, we also develop models based on some of the other machine learning techniques, such as neural networks (56), and use them as benchmarks. If needed, to improve model performance we will perform model building in RF models to identify and include the most important parameters (38). We will use techniques such as cross-validation (e.g., leave-one-out) and bootstrapping to examine the generalizability of the models and acquire confidence intervals for the predicted values. Lastly, we will compare the best performing models obtained for both ON and OFF medications and their most important contributing parameters to further investigate the interaction of medications and stimulation frequency.

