Aim 2.2. Similar to Aim 2.1, in this sub-Aim we conduct regression analysis to predict gait parameters. However, in this sub-Aim, gait parameters are predicted on low and high frequency in the context of ON and OFF medication conditions using baseline bradykinesia, tremor, and gait sensor measurements, plus MDS-UPDRS III rigidity and axial sub scores. Patient and disease characteristics will be used as regressors. Again, models will be based on RF classifier, where other modeling techniques, such as neural networks, will be used as benchmarks. The best performing parameters identified in Aim 2.1 will be used to guide the model building in this sub-Aim. Also, aforementioned performance enhancing techniques will be used, if possible, and confidence intervals will be generated using bootstrapping. These models will be able to predict the best stimulation frequency and contact pairs for the patient immediately after baseline evaluations and provide a confidence level. Similar to Aim 2.1, we will

develop these models with and without accounting for PD medications to further quantify their impact and provide additional options for patients.

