10.4 PROTOCOL AMENDMENT HISTORY

The table below is intended to capture changes of IRB-approved versions of the protocol, including a description of the change and rationale. A Summary of Changes table for the current amendment is located in the Protocol Title Page.

Version	Date	Description of Change	Brief Rationale
1.0	4/15/19	Original	N/A
1.1	10/29/19	Updated eligibility criteria, editorial clarification, LD dose maximum 300mg, shortened off period for chronic DBS subject experiencing intolerable symptoms, additional of external referral sources and on-line outreach	Clarity, patient comfort, to meet recruitment goals
1.2	1/8/20	Addition of second SAW test for every trial, change source of LD tablets from patient to NSUH pharmacy.	Ensure enough gait cycles are captured, remove drug supply/cost burden on participants.
1.3	1/22/20	IP supply changed from bottle to single dose blister packs; Removal of finger taps, touch nose, wrist rotation, and toe taps sensor assessments from Phase II	Availability through NSUH pharmacy; participant fatigue
1.4	3/2/20	Completion of one SAW test if participant is unable to do both; chronic DBS eligibility revised from one year to 6 months; administration of additional levodopa in event of wearing off	Subject safety and comfort, facilitate recruitment, maintain levodopa ON state during assessments
1.5	8/4/20	Add Visit 3 to Schedule of Activities; Addition of COVID-19 safety measures including preappointment screening, COVID-19 testing and remote consent.	Clarity; COVID-19 pandemic
1.6	12/22/20	Chronic DBS patient eligibility revised from 6 months to 3 months	Facilitate recruitment
1.7	3/11/21	Fully vaccinated subjects exempt from COVID-19 testing prior to SV1; updated remote consent procedures; modified SOA to include optional use of clinical visit to complete electrode contact pair evaluation.	CDC guidance, subject convenience
1.8	4/15/21	Removal of blinding requirement for MDS-UPDRS Part III assessments	Blinded assessments are not factored into primary study analysis; not shown to be

			significant features on interim computational modeling (n=10)
1.9	8/12/21	Removal of non-English speaking criterion	Translation is sufficient to carryout study

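### Aim 2.2 reuses parameters chosen in Aim 2.1 on the same patients and the same 60 Hz outcomes, with no nesting stated, so its validated performance for 60 Hz gait can be optimistic

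*Combined protocol and SAP*

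**What the plan says.** All of the modelling text is in Section 9.4.2.

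- **Aim 2.1** sets out to "predict the gait parameters for patients on low frequency by using the gait sensor measurements obtained on high frequency". Age, gender and disease duration are added as regressors.
- Feature reduction is optional: "If needed, to improve model performance we will perform model building in RF models to identify and include the most important parameters".
- Validation is described in general terms: "We will use techniques such as cross-validation (e.g., leave-one-out) and bootstrapping to examine the generalizability of the models".
- Aim 2.1 ends with a comparison across medication states: "Lastly, we will compare the best performing models obtained for both ON and OFF medications and their most important contributing parameters".
- **Aim 2.2** has a wider outcome: "gait parameters are predicted on low and high frequency in the context of ON and OFF medication conditions".
- The inputs of Aim 2.2 also differ from those of Aim 2.1. Its models are built "using baseline bradykinesia, tremor, and gait sensor measurements, plus MDS-UPDRS III rigidity and axial sub scores", with characteristics of the patient and the disease added.
- The link between the two is one sentence: "The best performing parameters identified in Aim 2.1 will be used to guide the model building in this sub-Aim". What guiding the model building means is not defined.
- For Aim 2.2 the performance techniques of Aim 2.1 apply only where possible. Bootstrap confidence intervals are planned.

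Section 9.2 gives one cohort: 24 evaluable patients, 30 recruited. No section names the unit left out (patient or trial), a held-out set or an external cohort. None says that selection is repeated inside folds or bootstrap samples. The synopsis (Section 1.1) lists these models among the primary endpoints.

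**The concern.** Cross-validation gives an honest estimate only if the left-out patient played no part in building the model that predicts him or her. Choosing the predictors is part of building the model. In Aim 2.1 the choice is made by performance against 60 Hz gait. If it is made once, on everyone, and passed to Aim 2.2, each left-out patient's 60 Hz outcome has influenced the inputs before the Aim 2.2 loop begins. Leaving out whole patients in Aim 2.2 does not repair this, because the step lies upstream of the loop.

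The stake is the Aim 2.2 claim that response, and from it the better frequency, can be read from baseline sensors. Section 2.3.3 expects the models to support automated recommendations on frequency, and Section 2.1 expects the study to lead to a randomized trial. With 24 to 30 patients and dozens of candidate inputs, selection noise is large enough to matter.

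**Working it through.** **1. The plan's own figure.** Section 9.2: 15.79 × 0.03 / 0.14² = 0.4737 / 0.0196 = 24.17, stated as 24. Attrition: 24 × 1.2 = 28.8 (29), or 24 / 0.8 = 30. Both appear. The calculation is for a difference in mean gait speed. No figure is given for Aim 2.

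**2. The overlap between the sub-aims.**

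| | Aim 2.1 | Aim 2.2 |
|---|---|---|
| Patients | one cohort | the same cohort |
| Outcome | 60 Hz gait | 60 Hz gait and high-frequency gait |
| Inputs | high-frequency gait; age, gender, disease duration | baseline gait, tremor, bradykinesia, rating subscores; patient and disease characteristics |

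The 60 Hz outcome is shared in full. The inputs are not. A measure chosen on its high-frequency version enters Aim 2.2 in its baseline version, so the leak passes through the correlation ρ between the two versions.

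**3. Null simulation of the carry-over.** Assumptions: 40 candidates (the 20 measures of Section 9.4.2 × OFF and ON), independent of each other; five kept; one row per patient; ρ varied because the documents do not give it.

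- Outcome: pure noise. High-frequency inputs H: standard normal. Baseline inputs: B = ρH + √(1−ρ²)·e, with e standard normal.
- Rank the H versions against the outcome, keep five, fit a linear model on the matching B versions, and score it by leave-one-patient-out.
- Test the correlation r of predicted with observed: t = r√((n−2)/(1−r²)), one-sided 2.5%. At n = 24 the critical t is 2.074, so r must exceed 2.074/√(2.074² + 22) = 0.40.

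Selection made once on all patients, n = 24:

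| ρ | False significant | Median r | Median cross-validated R² |
|---|---|---|---|
| 0 | 3% | −0.11 | −0.43 |
| 0.3 | 6-9% | −0.02 | −0.36 |
| 0.5 | 14-15% | 0.15 | −0.22 |
| 0.7 | 29-30% | 0.30 | −0.08 |
| 0.9 | 54-59% | 0.44 | 0.09 |

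Ranges span repeated simulations. At 1000 runs the Monte Carlo error near 30% is √(0.3 × 0.7/1000) = 1.4 points. With selection redone in each fold the rate is roughly 2-8% (5-6% at ρ = 0.7, median r −0.06 to −0.09 across the settings run).

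**4. Sensitivity.**

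- n = 30, 40 candidates: 3%, 6%, 13%, 33% and 59% for the same ρ values.
- n = 24, 20 candidates: 19% at ρ = 0.7 and 29% at 0.9.
- Random forest, n = 24, 40 candidates, few runs: 12% at ρ = 0.7 (51 runs; error √(0.12 × 0.88/51) = 4.6 points) and 51% at ρ = 1 (49 runs). Nested at ρ = 0.7: 0 of 29.

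**5. A separate scenario.** Suppose Aim 2.2 also chose among its own baseline inputs outside the loop. A count of those inputs is 20 gait measures + 5 bradykinesia tasks + 3 tremor tasks + 10 rating items = 38; × 2 medication states = 76; + 3 characteristics = 79, about 80. Under noise, false significance is then 90-94%, with median r 0.55-0.58, against 9-10% and r of −0.04 to −0.08 when nested.

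**The case against.** Several points on the other side are sound.

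- **The inputs differ.** Aim 2.1 has no tremor, bradykinesia or rating-scale inputs and cannot rank them. For baseline gait the leak is indirect and vanishes at ρ = 0. Only age, gender and disease duration could pass across directly. This stands and limits the size.
- **High-frequency gait is not the Aim 2.1 outcome**, so the carry-over does not bear directly on that half of Aim 2.2. This stands.
- **The effect depends on the metric.** Judged by R², the carry-over alone stays below zero in the median up to ρ = 0.7. The plan names no metric, so this does not settle the matter.
- **The wording is loose.** The text also uses the word parameters for gait outcomes, and the verb guide could mean little. On the outcome reading, a choice based on these patients' results would still precede validation, but the simulation does not measure that case.

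A reader might go further than the documents allow:

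- *That features are selected outside the validation loop throughout.* The order of the optional feature selection and the cross-validation is not stated either way. Only the carry-over is, as written, upstream of the Aim 2.2 loop. The 90% scenario therefore should not be attached to the quoted sentence.
- *That whichever of random forest and neural network does better will be reported.* The plan bases the models on random forest and calls the others benchmarks.
- *That interim modelling on 10 patients already fixed the features.* The version 1.8 entry in Section 10.4 is a rationale for removing a blinding requirement. Section 9.4.2 still includes the rigidity and axial subscores.

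The plan's remark that random forests resist overfitting does not answer the point. It concerns fitting, not selection made before validation.

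**Conclusion.** The concern holds in a limited form. The plan carries parameters chosen on 60 Hz gait into models that are validated on the same patients' 60 Hz gait, and it provides no nesting, held-out set or external cohort. Following it as written can make Aim 2.2 performance for 60 Hz gait optimistic. Under the stated assumptions the false-significance rate at n = 24 runs from about 3% (no correlation) through about 30% (ρ = 0.7) to 54-59% (ρ = 0.9), against roughly 2-8% when nested. A random forest appears less affected at ρ = 0.7 (12%, few runs).

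The size rests on an unknown correlation, independent candidates, five retained and one row per patient. The simulation does not measure accuracy in choosing the better frequency. Silence on nesting of the optional feature selection is a second gap, potentially larger, but the documents neither state nor exclude un-nested selection. This should be fixed before the Aim 2 analysis. It does not show that the Aim 2 results will be wrong.

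**What to change.** Amend the Aim 2.1 and Aim 2.2 text of Section 9.4.2 in one of three ways:

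1. Place the Aim 2.1 parameter selection, any Aim 2.2 feature selection, tuning and any choice of algorithm inside a single outer leave-one-patient-out loop, with all rows of a patient left out together. Repeat the same steps in each bootstrap sample.
2. Name the carried-over parameters before the outcome data are examined.
3. Remove the sentence that links the two sub-aims. If this is chosen, any Aim 2.2 feature selection still needs to be nested.

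In each case report the performance of the whole procedure and name the metric. A permutation test of the whole procedure is advisable: the simple correlation test ran at 5-6%, and at 9-10% with about 80 candidates, against a nominal 2.5% even when nested.

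Two other remedies are not recommended. Restricting Aim 2.2 to parameters from the earlier 20-patient work would not serve, because Section 4.2 shows that it used MDS-UPDRS III indicators and not sensor measures. Reporting separately the patients enrolled after the first 10 would leave only 14 to 20 (24 − 10 to 30 − 10).

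The cost is SAP wording and computing time, with no added patients or visits. Reported accuracy may be less favourable.

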2.3.3 ASSESSMENT OF POTENTIAL RISKS AND BENEFITS

Potential Benefits:

Expected Outcomes: Aim 1. We would have extensively investigated the impact of 60Hz stimulation on several gait spatiotemporal domains (e.g., pace, turning, postural sway) and relate it to other stimulation features (e.g., activated electrode contacts, therapeutic amplitudes) using wearable sensors. We will also determine the influence that levodopa has on 60Hz stimulation in the context of kinematic gait changes. These results can help facilitate the application of this stimulation to certain PD-DBS subpopulations. Aim 2. Our results will allow for instantaneous recommendations by artificial intelligence on which stimulation frequency is best suitable for a subject based on *a priori* sensor measurements of motor symptoms. The ranking provided can guide clinical evaluations and potentially reduce the amount of time needed for programming by changing the “trial and error” paradigm to a sensor guided paradigm with either 60Hz or HFS initiated from the outset.

Potential Risks:

Subjects will be closely monitored following administration of carbidopa/levodopa 25/100mg tablet(s) to ensure any side effects are minimized and addressed immediately.

Any stimulation side effect will immediately be alleviated with reduction in DBS amplitude. All assessments will be done at amplitudes below the side effect threshold. Furthermore, all sensor assessments will be conducted in a control setting with the research coordinator and Principal investigator present at all times to minimize risk any risk of falling during the gait assessment.

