9.2 SAMPLE SIZE DETERMINATION

To determine the sample size, we averaged the gait parameters (across all age groups) along with pooled variance captured on the APDM inertial sensors for healthy subjects (53) and PD patients with gait disorder (54) and computed a reasonable sample size of 24 (which equates to a Cohen's $d=0.8$) with a power of 0.80 and level of significance of 0.05. Assuming a 20% attrition rate, we will attempt to recruit 30 patients.

Sample Size estimation

$(\alpha) = 0.05, Z_\alpha = 1.96$
 $(\beta) = 0.80$

$$n = \frac{2(Z_a + Z_{1-\beta})^2 \sigma^2}{\Delta^2}$$

Reference Gait values for healthy individuals using APDM sensors

Age Groups	n	mean	STD	Variance
		normalized speed		
20-29	41	1.14	0.12	0.0144
30-39	41	1.16	0.14	0.0196
40-49	42	1.14	0.16	0.0256
50-59	45	1.21	0.14	0.0196
60-69	51	1.13	0.12	0.0144
70-89	72	0.86	0.23	0.0529

Ages 50-89: Mean Velocity - 1.06

Calculated Pooled Variance for Ages 50-89- 0.03

Calculated Pooled Variance for All ages – 0.03

Gait Parameters for PD patients with gait disorder (FOG- & FOG +) using APDM sensors

Walking Measure		Single Task Mean \pm STD
Stride Length (m)	FoG-	1.06 \pm 0.15
	FoG+	0.92 \pm 0.22
Stride Velocity (m/s)	FoG-	0.99 \pm 0.18
	FoG+	0.86 \pm 0.21

Average age 68 STD 8.4 (FOG -)

Average Age 69 STD 7.9 (FOG+)

Mean Velocity – 0.925 (FOG- & FOG+)

de Souza Fortaleza AC, Mancini M, Carlson-Kuhta P, King LA, Nutt JG, Chagas EF, Freitas IFJ, Horak FB. Dual task interference on postural sway, postural transitions and gait in people with Parkinson's disease and freezing of gait. *Gait Posture*. 2017;56:76-81.

Effect Size 1.06-0.925 = .14

$N = 15.79 (.03)/ (.14)^2 = 24 + 20\% \text{ attrition} = \text{total study recruitment } 29 \text{ subjects.}$

Final Study N= 30 subjects

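### The bootstrap confidence intervals planned for the random-forest gait predictions would, as ordinarily built, understate the uncertainty for an individual patient, and the patient-level confidence level is undefined

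*Combined protocol and SAP*

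**What the plan says.** All of the relevant method is in section 9.4.2 of the combined protocol and SAP.

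- **Aim 2.1** predicts gait on 60 Hz from gait on high frequency with a random forest, in which "predictions for any new observation are obtained from averaging the predictions of individual trees". On checking, it says "We will use techniques such as cross-validation (e.g., leave-one-out) and bootstrapping to examine the generalizability of the models", and the same sentence adds that these techniques will "acquire confidence intervals for the predicted values".
- **Aim 2.2** predicts gait on both frequencies from baseline sensor and clinical data. It states that "confidence intervals will be generated using bootstrapping". The next sentence says the models will identify the best frequency and contact pairs for a patient "immediately after baseline evaluations and provide a confidence level".
- **Section 2.3.3** gives the intended use: "Our results will allow for instantaneous recommendations by artificial intelligence on which stimulation frequency is best suitable for a subject".

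Section 1.1 lists the model that predicts best frequency among the primary endpoints. The documents do not state the resampling unit or the bootstrap algorithm. They do not say whether an interval targets the mean prediction or an individual's outcome, or how the confidence level is calculated. They mention no prediction interval, coverage check or calibration check.

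**The concern.** The interval named and the use intended answer different questions. A forest prediction is an average and estimates the mean outcome of patients with given baseline values. Bootstrapping that average shows how far the estimate would move with a different training sample. A recommendation for one patient also depends on how far that patient's own gait departs from the mean, and with 24 to 30 patients this may well be the larger part of the error.

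If the narrower interval were reported as the uncertainty for an individual, or if the confidence level were read from the spread of bootstrap forests, the model would look more dependable than it is. Section 2.1 presents the study as preparation for a randomized trial of selecting patients for 60 Hz before surgery, so the overstatement would carry into that design.

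**Working it through.** **1. The plan's own figure.** Section 9.2 gives n = 2(1.96 + 0.85)² × 0.03 / 0.14² = 15.79 × 0.03 / 0.0196 = 24.17, stated as 24. With attrition, 24 × 1.2 = 28.8, stated as 29, and the final figure is 30. The arithmetic reproduces. It was derived for a difference in mean walking speed and sets no accuracy or coverage target for Aim 2. Only the patient numbers, 24 and 30, are used below.

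**2. The two variances.** Let σ² be the variance of patients around the true mean and hσ² the estimation variance of the fitted mean. A confidence interval for the mean reflects hσ². A new patient's outcome differs from the prediction with variance σ²(1 + h).

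**3. Normal-theory guide, without a forest.** Take h = p/n for p fitted parameters and t as the 97.5% point on n − p degrees of freedom. The prediction interval is √(1 + h)/√h times as wide as the confidence interval. The confidence interval covers a new outcome with probability P(|T| ≤ t√(h/(1 + h))).

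| n | p | width ratio | coverage of an individual outcome |
|---|---|---|---|
| 24 | 1 | 5.00 | 32% |
| 24 | 4 | 2.65 | 56% |
| 24 | 10 | 1.84 | 74% |
| 30 | 1 | 5.57 | 28% |
| 30 | 10 | 2.00 | 69% |

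**4. Random-forest simulation.** The following are assumed, because the documents give none of them: R-squared 0.3 to 0.7, 10 predictors (4 informative), and whole patients resampled. Each run used 60 bootstrap forests of 50 trees, 12 data sets and 300 new patients per data set. Coverage of a new patient's outcome, nominal 95%, with mean width in brackets:

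| n | R² | bootstrap percentiles of averaged prediction | quantiles across single trees | out-of-bag residual interval | width ratio, residual to bootstrap |
|---|---|---|---|---|---|
| 24 | 0.3 | 41.9% (1.99) | 89.1% (6.34) | 95.5% (8.01) | 4.0 |
| 24 | 0.5 | 41.8% (1.53) | 87.4% (4.73) | 95.3% (5.86) | 3.8 |
| 24 | 0.7 | 41.0% (1.15) | 86.9% (3.57) | 95.4% (4.61) | 4.0 |
| 30 | 0.5 | 43.6% (1.47) | 90.5% (4.78) | 97.7% (6.36) | 4.3 |

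Other settings at n = 24 agree. With 20 predictors and R-squared 0.3 or 0.6, the bootstrap interval covered 40% and a leave-one-patient-out residual interval 90-91%. A further simulation with R-squared 0.3 to 0.6 gave 38-48% and 95-98%.

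**5. One possible confidence level.** Suppose the outcome is the 60 Hz minus HFS difference and confidence is the share of bootstrap forests that favour the chosen frequency. The simulation in step 4 then gives:

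| n | R² | mean stated confidence | choice correct | patients at ≥95% confidence | correct among these |
|---|---|---|---|---|---|
| 24 | 0.3 | 76% | 57% | 15% | 69% |
| 24 | 0.5 | 80% | 62% | 26% | 76% |
| 24 | 0.7 | 78% | 64% | 19% | 82% |
| 30 | 0.5 | 79% | 64% | 21% | 83% |

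The runs are small and no Monte Carlo error was calculated, so the figures are approximate.

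**The case against.** The strongest reply is that the plan is silent rather than wrong. A reader might infer that it offers these intervals as prediction intervals, but it never uses that term. A reader might also infer that the confidence level is read from the bootstrap. The text only places the two in adjacent sentences and gives no derivation. Nor does the wording rule out a version that carries residual spread: quantiles across single trees covered 87-91% in step 4. All of this stands, and it is why the point is limited to the ordinary implementation.

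Leave-one-out cross-validation is planned and would expose part of the individual error. This stands in part: its stated purpose is generalizability, and nothing ties it to the confidence level. The plan also does not say that the unit left out is the patient. Section 4.1 gives 8 stimulation trials in each of two medication conditions, so 8 × 2 = 16 per patient.

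A reader might further infer that participants would act on misleading recommendations. The documents do not support that. Sections 6.1.1 and 7.1 return participants to their original settings and regimen after each visit, and section 2.3.3 describes an expected outcome, not a trial procedure.

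Finally, it is tempting to say that confident recommendations would be right only about half the time. That result comes from a scenario in which the frequency difference was made independent of the predictors, so 50% is true by construction. Even there, only 20% of patients reached 80% confidence. With some signal present, step 5 shows 57-64% correct overall: overconfident, but not a coin toss.

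**Conclusion.** The point holds in a limited form. The only interval method named for Aim 2 is a confidence interval for predicted values, while the stated use is a recommendation for one patient with a confidence level. Implemented in the ordinary way, a nominal 95% interval would cover a new patient's outcome about 40-50% of the time, against roughly 90-98% for residual-based intervals about four times as wide.

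These figures assume 24 patients (30 in one run), R-squared of 0.3 to 0.7, and 10 or 20 predictors. The documents give no R-squared, residual variance or predictor count, so the exact size cannot be derived from them. The direction did not change under any assumption tried for this type of interval.

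Because coverage can run from about 40% to above 90% on a choice the plan leaves open, the uncertainty statement attached to a primary endpoint is not prespecified. The consequence falls on the study's conclusions and on the later trial. The Aim 1 mixed-model analysis is unaffected.

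**What to change.** Amend section 9.4.2, Aims 2.1 and 2.2, as follows.

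- **Intervals.** State that individual-level intervals, for each predicted gait value and for the 60 Hz minus HFS difference, will be patient-level prediction intervals built from leave-one-patient-out residuals (for example jackknife+). Hold out all of a patient's trials together. Report empirical coverage beside nominal coverage. Bootstrap intervals may stay if labelled as uncertainty in the mean prediction.
- **Confidence level.** Define it from out-of-patient predictions, not from the bootstrap spread of the fitted mean.
- **Calibration.** Report the overall cross-validated agreement between stated confidence and correct choice. A finely binned table would be imprecise: a bin with 20% of 24 patients holds about 5, and a proportion of 0.7 then has a standard error of √(0.7 × 0.3 / 5) = 0.20.
- **Level.** Choose the nominal level with the sample in mind. For a simple residual interval at 95%, the rank needed is 0.95 × (24 + 1) = 23.75, rounded up to 24, so the single largest residual sets the width. At 80% it is 0.80 × 25 = 20, the 20th of 24.

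The cost is SAP wording, refitting with each patient left out, and visibly wider intervals. No new data are needed.
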